4.2.2 BLOOD SAMPLE FOR BIOMARKER ASSESSMENT

This will be collected at each visit, plasma will be separated by PBMC PI laboratory and samples will be kept frozen at -80C until use.

4.3 METHOD OF TREATMENT ASSIGNMENT

Participants will be and randomly assigned (1:1) to either the baloxavir + oseltamivir group, or the placebo + oseltamivir group. Before randomization, patients will be stratified by hospitalization (yes or no), influenza type A (yes or no). To maintain blinding, patients in the oseltamivir group will receive baloxavir-matched placebo.

The design randomization schema will be developed and managed by the Weill Cornell investigational pharmacy. Unblinding will be done when last patient completed the study follow up period.

Study Treatment: The investigational medicinal product (IMP) for this study is baloxavir in combination with oseltamivir.

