3. STUDY DESIGN

3.1 DESCRIPTION OF THE STUDY

This is a randomized double-blind placebo-controlled pilot study of the efficacy and safety of baloxavir in combination with oseltamivir (SOC) for the treatment of influenza in allogeneic stem cell transplant patients.

30 SCT recipients with influenza will take part in the study. Participants will be randomly assigned (1:1) to either baloxavir + oseltamivir or baloxavir-matched placebo +oseltamivir. Randomization will be performed by research pharmacy using an interactive web randomizer. Before randomization, patients will be stratified by hospitalization status (yes or no), influenza type A (yes or no).

Patients in the baloxavir combination arm will receive weight-adjusted baloxavir (40 mg for patients weighing <80 kg and 80 mg for those weighing \geq 80 kg) at baseline and at day 4 and day 7. They will also receive oseltamivir 75 mg twice daily for 10 days.

Patients in the baloxavir-matched placebo + oseltamivir arm will receive baloxavir-matched placebo at baseline and at day 4 and day 7 and oseltamivir 75 mg twice daily for 10 days.

Nasopharyngeal swabs will be collected on days 1 (at diagnosis, pre-meds), 2, (optional visit), 4, 7 and 10 for viral quantitation and viral sequencing. Influenza virus polymerase and neuraminidase sequencing will be also performed in all patients. Patients will have follow-up visits day 15 (+/- 2 days) and day 30 (+/- 2 days, EOT). Patients who will not clear the virus by day 10 will perform additional NP swabs at these visits.

Paracetamol (acetaminophen; maximum 3000 mg per day) or NSAIDS can be given for severe discomfort or fever. No other antiviral drugs for the treatment of influenza, will be permitted, except antibiotics for the treatment of suspected bacterial infections.

For the first 10 days, patients will receive a daily call from one member of the study team to review symptoms and severity scale.

To assess the **time to improvement of individual influenza symptoms** (with modification for preexisting symptoms), participants will be given a diary to self-assess the severity of seven influenza-associated symptoms on a four-point scale. To evaluate patient-reported **time to return to pre-illness health status**, patients will also rate **daily the interference of influenza symptoms in daily activities** on a 5-point severity scale.

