3.2 END OF STUDY AND LENGTH OF STUDY

The end of this study is defined as the date when the last patient, last visit (LPLV) has occurred, patient has become lost to follow up, patient has withdrawn consent, or patient has completed at least 1 months of follow-up after randomization. The end of the clinical part of the study is expected to occur two months after the last patient is enrolled. After that the study will be open for analysis only. In addition, the Investigator may decide to terminate the study at any time.

The total length of the study, from screening of the first patient to the end of the study, is expected to be approximately 24 months.

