4.2 SAMPLE COLLECTION AND PROCESSING

4.2.1 NASOPHARYNGEAL SAMPLING AND VIROLOGICAL ASSAYS

Two nasopharyngeal swabs will be collected at each visit and put immediately into viral transport medium and frozen. Pharyngeal swabs will be collected when if it is not possible to collect nasopharyngeal swabs. At the end of the clinical study period, samples will be used for viral sequencing and virological assessment.

Viral RNA in pre- and last post-treatment swab samples will be extracted using conventional RNA extraction kit without virus amplification and used for viral RNA quantification by q-PCR and for viral sequencing. Swabs will also be used to calculate viral titers by plaque assays on MDCK cells.

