4.5.8 LABORATORY, BIOMARKER, AND OTHER BIOLOGICAL SAMPLES

Samples for the following laboratory tests will be sent to the study site's local laboratory for analysis as routinely done for standard of care:

- Hematology: WBC count, RBC count, hemoglobin, hematocrit, platelet count
- Chemistry panel (serum or plasma): sodium, potassium, magnesium, chloride, glucose, BUN or urea, creatinine, total protein, albumin, phosphorus, calcium, total bilirubin, alkaline phosphatase, ALT, AST
- Pregnancy test
 - o All women of childbearing potential will have a serum pregnancy test at screening
 - o A woman is considered to be of childbearing potential if she is postmenarcheal, has not reached a postmenopausal state (≥ 12 continuous months of amenorrhea with no identified cause other

than menopause), and has not undergone surgical sterilization (removal of ovaries and/or uterus).

The following samples will be sent to the Investigator or a designee for analysis:

- NP swabs
- Blood samples for exploratory research on biomarkers
 - Exploratory biomarkers will include analysis of cfDNA, analysis of genes or gene signatures associated with influenza severity or recovery from influenza. This research will involve extraction of DNA, and genomic profiling through use of next-generation sequencing of a comprehensive panel of genes. NGS methods will not include whole genome sequencing (WGS).
 - Unless the patient gives specific consent for his or her leftover samples to be stored for optional exploratory research, biological samples will be destroyed when the final Clinical Study Report has been completed, with the following exception:
 - Blood samples collected for biomarker research will be destroyed no later than 10 years after the final Clinical Study Report has been completed.

When a patient withdraws from the study, samples collected prior to the date of withdrawal may still be analyzed, unless the patient specifically requests that the samples be destroyed or local laws require destruction of the samples. However, if samples have been tested prior to withdrawal, results from those tests will remain as part of the overall research data.

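### The treatment code is released at the end of follow-up, with no requirement that the swab assays behind the co-primary endpoints be finished first and no stated masking of the laboratory

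*Combined protocol and SAP*

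**What the plan says.** **Unblinding.** Section 4.3 states: "Unblinding will be done when last patient completed the study follow up period". It attaches no condition about assay completion or data lock, and it does not say who receives the code. The same section has the investigational pharmacy develop and manage the randomization schema.

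**Timing of the assays.** Section 4.2.1 states: "Two nasopharyngeal swabs will be collected at each visit and put immediately into viral transport medium and frozen". It continues: "At the end of the clinical study period, samples will be used for viral sequencing and virological assessment". The extracted RNA is then "used for viral RNA quantification by q-PCR and for viral sequencing", and the swabs also supply the plaque-assay titers.

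**Milestones.** Section 3.1 and Appendix 1 put the last visit at day 30, with a window of 2 days either way. Section 3.2 adds: "The end of the clinical part of the study is expected to occur two months after the last patient is enrolled". It then says: "After that the study will be open for analysis only".

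**Who handles the samples.** Section 4.5.8 lists the nasopharyngeal swabs under this sentence: "The following samples will be sent to the Investigator or a designee for analysis". For sequence analysis, Statistical Considerations names a section director at NIAID/NIH.

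**What depends on the assays.** Section 2.1 builds both co-primary endpoints on the day 1 to day 10 change in viral RNA load by qRT-PCR. The plaque assay is added for the between-arm comparison. Secondary endpoints 1 to 4, 8 and 9 also rest on the stored swabs. Section 3.1 describes the trial as double-blind.

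**The concern.** A double-blind trial should protect the measurement of its main outcome as well as its conduct in the clinic. Here the clinical phase is masked, but the central measurement is made from frozen samples at the end, and the rule for breaking the code does not wait for it.

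Several steps in that measurement involve judgement:
- counting plaques;
- deciding whether a weak signal is detectable;
- repeating an odd result;
- choosing which of the two swabs from a visit to use, or whether a pharyngeal substitute is acceptable;
- declaring a sample unusable.

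The last of these has a direct consequence. The primary analysis set in Statistical Considerations requires viral load at both baseline and day 10, so rejecting one of those samples can remove a patient. With about 15 patients per arm, a few such decisions count.

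If they were made with the arms known, any resulting bias could not be measured or excluded afterwards. Statistical Considerations says the summaries will help plan future studies, so a bias would be carried forward.

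**Working it through.** **1. Order of events.** Count days from the last enrolment. Assume that enrolment is day 1, that the last patient enrolled is the last to finish, and that a month is 30 days.

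| Event | Source | Day |
|---|---|---|
| Last patient completes follow-up; code released | 4.3 with 3.1 and Appendix 1 | 28 to 32 |
| Clinical part ends | 3.2 | about 60 |
| Virological assays start | 4.2.1 | end of the clinical study period |

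The documents do not define the clinical study period, so there are two readings.

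- *It is the clinical part of section 3.2.* The gap is 60 − 32 = 28 to 60 − 28 = 32 days, or about 30. The assays start after the code is released.
- *It ends when follow-up ends.* The gap is 0 days. Code release and the start of the assays share one trigger, and nothing requires the assays to come first.

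Neither reading requires final assay results before unblinding.

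**2. Search for a safeguard.** Sections 4.2.1, 4.3 and 4.5.8 and Statistical Considerations are where one would expect masked laboratory staff, arm-neutral sample labels, restricted release of the code, or a data lock before unblinding. None of these is stated there or elsewhere.

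**3. The plan's own figures.** Statistical Considerations gives 80% power with 15 per arm, two-sided 0.05, for a within-arm change of 2.33 log10 and a between-arm effect of 1.1 SD.

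- Paired t-test, n = 15, SD of differences 3: detectable change 2.334 log10; power at 2.33 is 79.9%. This reproduces.
- Two-sample t-test, 15 per arm: detectable effect 1.06 SD, which rounds to 1.1; power at exactly 1.1 is 82.8%.

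The point does not depend on these figures. They do show that the plan in effect uses 3 log10 as the SD of the change, and that value is borrowed below.

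**4. Illustration of size.** Suppose there is no true treatment difference, but measurement shifts one arm systematically by δ relative to the other.

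- Standard error of the difference in mean change = 3 × √(2/15) = 1.095 log10.
- Two-sample t-test, df = 15 + 15 − 2 = 28, two-sided 0.05, critical value 2.048.
- Noncentrality = δ / 1.095. The false-positive rate is the probability that a noncentral t with 28 df exceeds 2.048 in absolute value.

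| δ (log10) | Fold error (10^δ) | Noncentrality | False-positive rate |
|---|---|---|---|
| 0 | 1 | 0 | 5.0% |
| 0.1 | 1.3 | 0.091 | 5.1% |
| 0.2 | 1.6 | 0.183 | 5.4% |
| 0.3 | 2.0 | 0.274 | 5.8% |
| 0.5 | 3.2 | 0.456 | 7.3% |
| 1.0 | 10 | 0.913 | 14.3% |

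The documents give no basis for any particular δ. The table is a range of assumptions, not an estimate. It describes only the between-arm comparison; the first co-primary endpoint is a change within each arm and has no between-arm error rate.

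**The case against.** The strongest reply is that nothing in the plan prescribes unblinded assay. Four stronger readings are tempting, and the documents do not support them.

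- *A reader might infer that the assayers will know the allocation.* No section says so. Section 4.3 leaves the schema with the pharmacy and does not name who is unblinded. The plan fails to exclude knowledge of the arms, which is a weaker statement.
- *A reader might infer a fixed one-month gap.* That requires equating the clinical study period of 4.2.1 with the clinical part of 3.2, whose two months are only expected. The gap may be zero.
- *A reader might place all the virology with the investigator's team.* Statistical Considerations gives sequence analysis to an outside NIAID/NIH group, so the variant endpoint is less exposed to the team, although masking of that group is not stated either.
- *A reader might add the open choice between the paired t-test and the Wilcoxon signed rank test.* That choice applies within each arm and is a separate prespecification matter. Changing the time of unblinding would not settle it.

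Other mitigating facts also stand. qRT-PCR is largely instrument-read, and plaque counting enters the primary endpoints only through the between-arm comparison. Statistical Considerations calls all between-arm comparisons exploratory and the study probably under-powered, and section 3.1 calls it a pilot. The larger shifts in the table are 3.2-fold and 10-fold errors, systematic by arm; a two-fold error or less leaves the rate below 6%.

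One could also note that the extra swabs for patients who have not cleared virus by day 10 (3.1, and Appendix 1 footnote f) imply some viral testing during follow-up. The assay is not named, and 4.2.1 still puts quantification at the end.

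These facts lower the stakes. None of them makes unblinding wait for the virology or masks the laboratory.

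**Conclusion.** The concern holds in a limited form. As written, the code may be released before, or at the same time as, the start of the assays that supply the co-primary endpoints, and no provision keeps the laboratory masked. The assayers could know the allocation; the documents do not establish that they would.

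The possible effect runs from negligible to material: a false-positive rate of 5.1% to 14.3% for the exploratory between-arm test, over assumed shifts of 0.1 to 1.0 log10. This rests on an SD of change of 3 log10, 15 evaluable patients per arm and a shift in one direction only. The larger cost is to credibility, because masking cannot be restored once the code has been released.

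For a pilot with exploratory between-arm comparisons and a mainly instrument-read assay, this is a cheap improvement that should be made. It is not a defect that invalidates the design.

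**What to change.** - **Section 4.3:** replace the unblinding sentence with a rule that the treatment code is released only after all qPCR, plaque-assay and sequencing results are final and the clinical and virology data are locked.
- **Section 4.2.1:** state that samples are assayed under coded labels by staff without access to the allocation. Fix in advance which swab is used at each visit and when a test is repeated.

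The change needs a short amendment before the code is released. It requires no additional patients, swabs or assays and alters no sample size or power figure. The price is that unblinding waits for the laboratory; the documents give no turnaround time, so the length of that wait is unknown. The documents also do not describe laboratory staffing, so the sponsor should confirm that staff without access to the allocation are available.

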4.3.1 STUDY TREATMENT FORMULATION, PACKAGING, AND HANDLING

4.3.1.1 Xofluza

Xofluza will be supplied by the Genentech, Inc. as tablets.

For information on the formulation and handling of Xofluza, see the Xofluza Investigator's Brochure.

4.3.1.2 Placebo

Baloxavir-matched placebo will be supplied by Genentech, Inc. as tablets.

4.3.1.3 Oseltamivir

Oseltamivir will be supplied by Genentech, Inc. as 75 mg tablets for oral administration. For information on the formulation, packaging, and handling of Oseltamivir see the local prescribing information for Oseltamivir.

4.3.2 STUDY TREATMENT DOSAGE, ADMINISTRATION, AND COMPLIANCE

The treatment regimens are summarized in Section 3.1.

Treatment will be self-administered in case of outpatient, the first dose will be taken during the clinic visit.

For hospitalized patients, treatment will be administered by a trained nursing professional.

Any overdose or incorrect administration of baloxavir or oseltamivir should be noted in the patient's medical records and reported according to Section 5.5 (Special Situations Reports). Adverse events associated with an overdose or incorrect administration of any of the study treatments should be recorded in the patient's medical records.

4.3.2.1 Baloxavir and Oseltamivir

The treatment regimens are summarized in Section 3.1.

Patients in the baloxavir combination group will receive an oral dose of baloxavir at baseline (40 mg for patients weighing <80 kg and 80 mg for those weighing ≥80 kg) and at day 4 and 7. They will also receive oseltamivir 75 mg twice daily for 10 days.

4.3.2.2 Placebo and Oseltamivir

Patients in the standard-of-care group will receive oseltamivir 75 mg twice daily for 10 days and an oral dose of baloxavir-matched placebo at baseline and at day 4 and 7.

4.4 CONCOMITANT THERAPY, PROHIBITED FOOD, AND ADDITIONAL RESTRICTIONS

Concomitant therapy consists of any medication (e.g., prescription drugs, over-the-counter drugs, vaccines, herbal or homeopathic remedies, nutritional supplements) used by a patient in addition to protocol-mandated treatment from 7 days prior to initiation of study treatment to the treatment discontinuation visit. All such medications should be reported to the investigator and recorded in the patient's medical records.

4.4.1 PERMITTED THERAPY

All therapies required for the management of the patient's acute illness are permitted except for those listed below in Section 4.4.3 (Prohibited Therapy).

4.4.2 CAUTIONARY THERAPY

Polyvalent cation-containing products may decrease plasma concentrations of Xofluza. Thus, dairy products, calcium-fortified beverages, polyvalent cation-containing oral laxatives or oral antacids, and oral supplements containing iron, zinc, selenium, calcium, or magnesium should not be taken with Xofluza, where possible.

4.4.3 PROHIBITED THERAPY

Use of the following concomitant therapies is prohibited as described below:

- Investigational antimicrobial therapy (other than the protocol-mandated study treatment) is prohibited within 5 half-lives or 30 days (whichever is longer) prior to initiation of study treatment and during the study
- Concomitant use of herbal therapies is prohibited as their pharmacokinetics, safety profiles, and potential drug-drug interactions are generally unknown

4.5 STUDY ASSESSMENTS

The schedule of activities to be performed during the study is provided in Appendix 1. All activities must be performed and documented for each patient. Patients will be closely monitored for safety and tolerability throughout the study. Patients should be assessed for toxicity prior to each dose; dosing will occur only if the clinical assessment and local laboratory test values are acceptable.

4.5.1 INFORMED CONSENT FORMS AND SCREENING LOG

Written informed consent for participation in the study must be obtained before performing any study-related procedures (including screening evaluations). Informed Consent Forms for enrolled patients and for patients who are not subsequently enrolled will be maintained at the study site.

All screening evaluations must be completed and reviewed to confirm that patients meet all eligibility criteria before enrollment. The investigator will maintain a screening log to record details of all patients screened and to confirm eligibility or record reasons for screening failure, as applicable.

4.5.2 MEDICAL HISTORY, CONCOMITANT MEDICATION, AND DEMOGRAPHIC DATA

Medical history, including clinically significant diseases, surgeries, cancer history (including prior cancer therapies, current cancer stage, and procedures), menstrual

history, fertility history, and puberty history, will be recorded at baseline. In addition, all medications (e.g., prescription drugs, over-the-counter drugs, vaccines, herbal or homeopathic remedies, nutritional supplements) used by the patient in addition to protocol-mandated treatment within 7 days prior to initiation of study treatment until 30 days after the final dose of study drug will be recorded. At the time of each follow-up physical examination, an interval medical history should be obtained and any changes in medications and allergies should be recorded.

Demographic data will include age, sex, and self-reported race/ethnicity.

4.5.3 PHYSICAL EXAMINATION

A complete physical examination, will be performed at screening and other specified visits. Any abnormality identified at baseline will be recorded in the patient's medical records.

Limited, symptom-directed physical examinations should be performed at specified postbaseline visits and as clinically indicated. Changes from baseline abnormalities should be recorded in patient notes. New or worsened clinically significant abnormalities should be recorded as adverse events in the patient's medical records.

4.5.4 VITAL SIGNS

Vital signs will include measurements of respiratory rate, pulse rate, and systolic and diastolic blood pressure, and temperature and will be performed at specified timepoints as outlined in the schedule of activities (see Appendix 1). They may be performed by a MN professional.

4.5.5 INFLUENZA DIAGNOSTIC TEST

For patients to be eligible for this study, a RT-PCR is required to be performed to inform a diagnosis of influenza. If a site has performed a RT-PCR test within the 24 hours prior to screening, the local RIDT or RT-PCR result can be used. Screening test for COVID-19 will also be performed before enrollment.

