CTCAE	Common Terminology Criteria for Adverse Events

Abbreviation	Definition
cfDNA	Cell-Free DNA
EC	Ethics Committee
eCRF	electronic Case Report Form
EDC	electronic data capture
HA	hemagglutinin complex
HIPAA	Health Insurance Portability and Accountability Act
ICH	International Council for Harmonisation
ICU	intensive care unit
iDMC	independent Data Monitoring Committee
IMP	investigational medicinal product
IND	Investigational New Drug (Application)
IRB	Institutional Review Board
LPLV	last patient, last visit
mITT	modified intent-to-treat (influenza) infected (population)
NA	neuraminidase
NAI	neuraminidase inhibitor
NCI CTCAE	National Cancer Institute Common Terminology Criteria for Adverse Events
PK	pharmacokinetic
PRO	patient-reported outcome
SCT	Stem cell transplant
SOC	standard of care
TCID ₅₀	50% tissue culture infectious dose
TQT	Thorough QT
TTAS	time to alleviation of symptoms
TTCI	time to clinical improvement
TTIIS	time to improvement of influenza symptoms
ULN	upper limit of normal
Vc/F	apparent volume of distribution for the central compartment

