4.1.1 INCLUSION CRITERIA

Patient must meet the following criteria for study entry:

- Adult patients: Signed informed consent by any patient capable of giving consent, or, where the patient is not capable of giving consent, by his or her legal/authorized representative
- Age \geq 18 years at the time of signing the Informed Consent Form/Accent Form
- Ability to comply with the study protocol, in the investigator's judgment
- Be defined as immunocompromised*, as defined by:
 1. Have received allogeneic bone marrow transplant, or
 2. Is currently receiving treatment with chemotherapy and/or CAR-T cell therapy for hematologic malignancies (e.g., leukemia, myeloma, lymphoma), or

- 3. Received treatment with chemotherapy and/or CAR-T cell therapy for hematologic malignancies (e.g., leukemia, myeloma, lymphoma) within the past 1 year.
- Tested positive for influenza infection after the onset of symptoms using a polymerase chain reaction (PCR)-based diagnostic assay.
- Presence of (a) fever ($\geq 38.0^{\circ}\text{C}$ per tympanic or rectal thermometer; $\geq 37.5^{\circ}\text{C}$ per axillary, oral or forehead/temporal thermometer) or (b) any influenza symptoms (cough, sore throat, nasal congestion, headache, feverishness or chills, muscle or joint pain, fatigue).
- The time interval between the diagnosis of influenza and the pre-dose examinations is 48 hours or less.
- For women of childbearing potential: Agreement to remain abstinent (refrain from heterosexual intercourse):

Women must remain abstinent or use contraceptive methods with a failure rate of $< 1\%$ per year during the treatment period and for 28 days after the last dose of study treatment.

Hormonal contraceptive methods must be supplemented by a barrier method.

A woman is considered to be of childbearing potential if she is postmenarcheal, has not reached a postmenopausal state (≥ 12 continuous months of amenorrhea with no identified cause other than menopause), and has not undergone surgical sterilization (removal of ovaries and/or uterus).

Examples of contraceptive methods with a failure rate of $< 1\%$ per year include bilateral tubal ligation, male sterilization, hormonal contraceptives that inhibit ovulation, hormone-releasing intrauterine devices, and copper intrauterine devices.

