Each Party shall monitor and, as applicable, request feedback from the other Party regarding AE report timeliness in accordance with its own procedures. The Parties agree to provide written responses in a timely manner to inquiries from the other Party regarding AE reports received outside the agreed upon Agreement timelines. If there is any detection of trends of increasing or persistent non-compliance to transmission timelines stipulated in this Agreement, both Parties agree to conduct ad hoc or institute a regular joint meeting to address the issue.

In case of concerns related to non-compliance of processes, other than exchange timelines, with this Agreement, the Parties will jointly discuss and collaborate on clarifying and resolving the issues causing non-compliance. Every effort will be made by the non-compliant Party to solve the non-compliance issues and inform the other Party of the corrective and preventative actions taken.

Upon justified request, given sufficient notice of no less than sixty (60) calendar days, an audit under the provisions of this Agreement can be requested by either Party. The Parties will then discuss and agree in good faith upon the audit scope, agenda and execution of the audit. The requesting Party will bear the cost of the audit.

STATISTICAL CONSIDERATIONS

The study plans to enroll a total of 30 allogeneic bone marrow transplant patients who will be randomized at 1:1 to the two study arms. The primary endpoint data will be analyzed on the basis of a modified intention-to-treat (ITT) principle for patients with viral loads measurements at both the baseline and day 10.

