- g. Perform assessments at any unscheduled visits based upon clinician's discretion.
- h. During the study treatment period (Day 1/Visit 1 to Day 10), all vital sign measurements (i.e., respiratory rate, pulse rate, peripheral oxygen saturation, systolic and diastolic blood pressures, and body temperature) should be recorded when on-site. For all other visits, the only vital signs measurement taken will be temperature. After day 10 vital sign measurements and specific assessments are to be recorded at the investigators' discretion (e.g., if symptoms and signs persist during follow-up).
- i. Presence or absence and type of respiratory support; oxygen saturation.
- j. See Section X for tests included in laboratory panels.

- k. Liver function test results to be reviewed by the investigator before Xofluza, or its matching placebo, is administered. On Day 1, prior blood results if tests conducted within 24 hours prior to screening. On Day 4 and day 7, blood liver chemistry panel should be reviewed before the patient will receive Xofluza or matching placebo on this study day.
 - l. Nasopharyngeal swabs for RT-PCR: RT-PCR for influenza and covid-19 should be performed at screening.
 - m. If a chest X-ray has not been taken within the 24 hours prior to screening, it will be performed per clinical provider decision. If the SOC is a chest CT scan, this can be used as alternative to the chest X-ray per clinical provider decision.
 - n. All women of childbearing potential will have a pregnancy test at screening (urine or serum).
 - o. Self-assessment of seven influenza-associated symptoms (cough, sore throat, headache, nasal congestion, feverishness or chills, muscle or joint pain, and fatigue) on a four-point scale (with 0 indicating no symptoms, 1 mild symptoms, 2 moderate symptoms, and 3 severe symptoms) twice daily from enrolment (day 1) until day 9 and once daily on days 10–15, and record their results in the patient diary.
 - p. Baloxavir treatment or Baloxavir-matched placebo dosing will occur on Day 1 and Day 4, with a further dose at Day 7
 - q. The SOC NAI (Oseltamivir) will be administered from Day 1 through Day 10.

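### The primary analysis set does not require detectable virus on Day 1, so patients who cannot show a fall can dilute the between-arm comparison

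*Combined protocol and SAP*

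**What the plan says.** **Analysis set.** The Statistical Considerations section bases the primary analysis on a "modified intention-to-treat (ITT) principle for patients with viral loads measurements at both the baseline and day 10". The List of Abbreviations expands mITT as "modified intent-to-treat (influenza) infected (population", but nothing says how infection is confirmed for analysis.

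**Eligibility test.** Section 4.1.1 requires: "Tested positive for influenza infection after the onset of symptoms using a polymerase chain reaction (PCR)-based diagnostic assay". A separate criterion there reads: "The time interval between the diagnosis of influenza and the pre-dose examinations is 48 hours or less". Section 4.5.5 opens with "For patients to be eligible for this study, a RT-PCR is required to be performed to inform a diagnosis of influenza" and continues: "If a site has performed a RT-PCR test within the 24 hours prior to screening, the local RIDT or RT-PCR result can be used". Appendix 1 note l states: "RT-PCR for influenza and covid-19 should be performed at screening". The Appendix 1 key lists RIDT, a rapid diagnostic test, separately from RT-PCR.

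**Related rules.** Section 4.1.2 excludes only patients with more than 48 hours of antiviral treatment before screening. Under Section 4.2.1, swabs are frozen and assayed after the clinical period. In Section 2.1 the second co-primary endpoint uses both qRT-PCR and plaque assay. Time to viral clearance refers to a detection limit, but no limit is stated and no value is assigned below it.

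**The concern.** An undetectable result is still a measurement. A patient who was PCR positive two days ago, and perhaps already treated, can have no detectable virus in the Day 1 swab. Nobody will know this at randomisation, because the study assays are run later. Under the Statistical Considerations wording that patient stays in the primary set with a change of about zero, and meets viral clearance at time zero if later samples are also negative. The exposure is greater for plaque assay, because a positive PCR does not guarantee replicating virus.

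Such patients pull both the within-arm change and the between-arm difference towards zero, and they widen the spread of changes in the arm with the larger fall. The pilot's declared product is per-arm summaries for planning later studies, and those would describe a mixture of patients who could and could not respond.

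**Working it through.** **Inputs from Statistical Considerations.** 15 per arm; two-sided 0.05; baseline mean 6.5 and SD 3 log10 vp/mL; fall of at least 3 log10 on oseltamivir alone; 80% power for 2.33 log10 within an arm and for 1.1 SD between arms.

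**Step 1: reproduce the plan (noncentral t).**
- Paired test: df 14, noncentrality (2.33/3) × √15. Power is 79.9%, so the plan's figure is reproduced, taking 3 as the SD of the change.
- Between arms: df 28. Power is 80% at 1.06 SD, which the plan rounds to 1.1 (power at 1.1 SD is 82.8%). In log10 units, 1.06 × 3 = 3.18.

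**Step 2: how many Day 1 negatives?** The documents give neither a rate nor an assay limit. A normal distribution with mean 6.5 and SD 3 puts 3.3%, 6.7% and 12.2% of baselines below assumed limits of 1, 2 and 3 log10. Multiplied by 15, that is about 0.5, 1.0 and 1.8 patients per arm. I use f = 5%, 10% and 20% as an assumed range; 20% lies above what this distribution gives.

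**Step 3: between arms, everyone kept.** A fraction f in each arm has change 0. The others have SD 3 and mean fall 3 (control) or 3 + 3.18 = 6.18 (combination).
- Expected difference = (1 − f) × 3.18.
- Variance in an arm with mean fall μ = (1 − f) × 9 + f(1 − f) × μ².

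For f = 10%: the difference is 2.862. The control variance is 8.1 + 0.09 × 9 = 8.91. The combination variance is 8.1 + 0.09 × 38.19 = 11.54. The pooled SD is √10.22 = 3.197. The noncentrality is 2.862 / (3.197 × √(2/15)) = 2.45, giving power 65.8%. Simulating the mixture directly gives 65% to 66%.

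**Step 4: Day 1 positives only.** The same t-test power at 1.06 SD, averaged over a binomial(15, 1 − f) number of positives in each arm.

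| f | Difference, everyone kept | Pooled SD | Power, everyone kept (formula / simulation) | Power, positives only |
|---|---|---|---|---|
| 0 | 3.18 | 3.00 | 80% / 80% | 80% |
| 5% | 3.02 | 3.11 | 72.9% / 72.5% | 78% |
| 10% | 2.86 | 3.20 | 65.8% / 65–66% | 75% |
| 20% | 2.54 | 3.31 | 52.8% / 52% | 69% |

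**Step 5: within-arm paired test, same method.**

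| f | True fall 2.33: everyone kept / positives only | True fall 3: everyone kept / positives only |
|---|---|---|
| 5% | 77.1% / 77.3% | 93.4% / 93.5% |
| 10% | 74.2% / 74.5% | 91.6% / 91.8% |
| 20% | 67.5% / 68.3% | 86.9% / 87.3% |

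Both sets lose power as f rises, but choosing between them changes the result by less than one point.

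**Step 6: numbers to randomise.** Keeping 15 Day 1 positives per arm would need 15/(1 − f), rounded up: 16, 17 or 19 per arm.

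**Step 7: eligibility text side by side.** Section 4.1.1 limits the time from diagnosis to the pre-dose examinations (48 hours). Section 4.5.5 governs reuse of a local result (24 hours). Note l schedules an RT-PCR and does not repeat that reuse. Two points stay open: what the RIDT mention is for when inclusion accepts only PCR, and whether a recent local RT-PCR replaces the screening RT-PCR. The second bears on f, because without a screening RT-PCR the only evidence of infection may be an earlier swab. No rule covers an earlier positive followed by a negative screening test.

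**The case against.** **Day 1 negatives may be rare.** Section 1.3 describes protracted shedding in transplant recipients, and Section 3.3.3 says they usually fail to clear infection after five days of oseltamivir. The 48-hour diagnosis and antiviral windows can also overlap. This stands as a reason to expect a low rate of RNA-negative samples. It is weaker for the chemotherapy and CAR-T patients whom Section 4.1.1 also admits, and for plaque assay. The range for f remains an assumption.

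**The comparison is already exploratory.** The plan calls itself likely under-powered and its between-arm comparisons exploratory. That lowers the stakes but does not justify avoidable dilution.

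A reader might infer more than the documents support:
- *That the infection criterion is stated in three incompatible ways.* One positive RT-PCR at screening satisfies Sections 4.1.1 and 4.5.5 and note l together, and the two time windows govern different things.
- *That a patient can enter on a rapid test alone.* Section 4.5.5 first requires an RT-PCR, its reuse sentence applies only where an RT-PCR was done, and Section 4.1.1 requires a PCR positive. The RIDT mention is a wording conflict and opens no valid route into the trial.
- *That four negatives of 15 take a 3 log10 fall to 3 × 11/15 = 2.2, below what the plan can detect.* The plan's 2.33 is the difference with 80% power and is not a cut-off. Four per arm is also well above the 0.5 to 1.8 in Step 2.

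**Conclusion.** The concern holds for the analysis set. The modified ITT wording admits Day 1 undetectable patients, the abbreviation list points to an infected population, and the entry and assay rules make such patients possible.

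The loss falls mainly on the between-arm comparison: from 80% power to about 73%, 65–66% and 52% at 5%, 10% and 20% undetectable with everyone kept, against 78%, 75% and 69% with Day 1 positives only. If no patient is undetectable, nothing is lost. For the within-arm tests the choice of set is immaterial.

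These figures assume the same f in both arms, a change of exactly zero for negatives, SD 3 among positives, a 3 log10 control fall, and a true effect of 1.06 SD. None of the documents supplies f, so this is a risk of conditional size and not a demonstrated loss. The eligibility wording is a separate, smaller matter of two points to reconcile.

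**What to change.** 1. Define the primary set for viral-load and clearance endpoints as randomised patients with detectable virus on the pre-dose Day 1 swab. Apply it separately for qRT-PCR and plaque assay, since RNA positivity does not ensure a plaque-positive baseline.
2. State each assay's detection limit and the value assigned below it.
3. Report all randomised patients with measurements as a sensitivity analysis. State separately how a missing Day 10 value is handled, because the Day 1 rule does not settle that.
4. Reconcile Sections 4.1.1 and 4.5.5 and Appendix 1 note l on the RIDT mention and on whether a recent local RT-PCR replaces the screening RT-PCR. State what follows if the two RT-PCR results disagree.

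The cost is protocol and SAP wording. No new assay is needed, because the Day 1 swab is already collected and quantified. Selecting on a pre-dose sample does not break the randomised comparison. The downside is that a few Day 1 negative patients leave the primary set, so fewer than 15 per arm may contribute unless the numbers in Step 6 are randomised.
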